7.1. Full Analysis Set

The Full Analysis Set will consist of all enrolled subjects in Part 2 who received at least one dose of study intervention. The Full Analysis Set will also be used for safety summary and for PD endpoints, except for MRI and histology endpoints.

7.2. Pharmacokinetics Analysis Set

The PK Analysis Set will consist of all subjects in the Full Analysis Set who have received BIO89-100, and have at least one serum BIO89-100 concentration measurement collected with full dose, and can adequately characterize the trough serum BIO89-100 concentrations.

7.3. MRI Analysis Set

The MRI Analysis Set will consist of all subjects in the Full Analysis Set who have measurable post-baseline MRI data.

7.4. Histology Biopsy Analysis Set

The Histology Biopsy Analysis Set will consist of all subjects in the Full Analysis Set who have both baseline (screening or eligible historical) and post-baseline biopsies.

8. Methods of Statistical Analysis

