4.2. Part 2 Study Design

Part 2 is an open-label cohort that will enroll 20 subjects with biopsy-proven NASH and fibrosis (NAS ≥ 4 , fibrosis stage F1 with high risk, F2 or F3). Subjects will either undergo a liver biopsy during screening or have a recent liver biopsy (within ≤ 24 weeks before Day 1, available to be evaluated for eligibility by the central reader) that meets study inclusion criteria. Eligible subjects will be treated with weekly (QW) SC injection of study intervention starting on Day 1 and continuing through Day 134 (20 weeks of treatment). Subjects will attend ambulatory clinic visits for dosing and evaluations and home visits for dosing⁹ as per the Schedule of Activities (SoA; Section 1.2.2, Table 6). Subjects will undergo a second liver biopsy within 14 days after the last dose of study intervention. Subjects will be followed up on Day 141 (1 week post last dose of study intervention) and Day 162 (4 weeks post last dose of study intervention, End of Study visit). Subjects who are found to be NAb-positive at the End of Study visit will be followed approximately every 3 months starting from when the site has been notified of the positive result, until: (1) neutralizing antibodies are no longer detectable or (2) the subject has been followed for a period of at least 1 year (± 4 weeks). More frequent testing (e.g., every month) or testing for a longer period of time may be requested in the event of safety-related concerns.

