8.4. Statistical Analyses

The statistical analysis plan (SAP) will be developed and finalized before database lock and will describe the subject populations to be included in the analyses, and procedures for accounting for missing, unused, and spurious data. Pooling of placebo subjects in Part 1 will be performed when applicable and will be specified in the analysis plan. This section is a summary of the planned

statistical analyses of the primary and secondary endpoints. Analysis of biomarkers and PD endpoints as well as their correlation with PK will be detailed in the SAP.

In general, summary descriptive statistics will be presented for demographics and baseline characteristics, safety endpoints, PK, and PD parameters. Descriptive statistics will include number of observations, mean, standard deviation, median, minimum, and maximum for continuous parameters. For PK and PD parameters, descriptive statistics will include the number of observations, arithmetic and geometric means, standard deviation, coefficient of variation, median, minimum, and maximum. Categorical parameters will be displayed using counts and percentages within each category.

For Part 1, while no formal hypothesis testing is planned for the primary objectives, the evaluation of potential efficacy will be determined based on the totality and pattern of data from the biomarker and PD endpoints. The assessment of biomarker and PD endpoints will employ 90% confidence intervals and significance testing for assessing within group changes and percentage changes from baseline and comparisons of the BIO89-100 doses to the pooled placebo group. Details will be provided in the SAP.

The correlation between relevant PK parameters and PD endpoints will be examined as will be detailed in the SAP.

Subjects with dose interruptions impacted by the COVID-19 pandemic will be noted in the listings. Subgroups including and excluding subjects with dose interruptions due to COVID-19 pandemic may be considered for both efficacy and safety analyses as appropriate.

For Part 2, endpoints of different histological responses will be summarized with the point estimates and 95% confidence intervals of the proportions of subjects who meet the response criteria using the biopsy analysis set.

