3.5. Sample Size and Power

For Part 2, no formal power calculations were used to determine the sample size in Cohort 7 and the number of subjects was chosen based on clinical experience with similar proof-of-concept histology studies and feasibility. This sample size accounts for an anticipated [REDACTED] of subjects who will not undergo the post-baseline liver biopsy (e.g., [REDACTED] to have paired liver biopsies). With a sample size of [REDACTED], the 95% confidence interval of the histological response rate would have a half-width no greater than [REDACTED] assuming the histological response [REDACTED]. The actual half-width will depend on the observed histological response rate [REDACTED].

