8.1.3. Analysis Visits and Visit Windowing

In general, all scheduled visits will be used as analysis visit for descriptive analysis tables and listings.

If a scheduled visit is missing, an unscheduled visit may be mapped to take its place if and only if it is within the visit window of the missing scheduled visit. The following table describes the visit mapping of unscheduled post-baseline visits in the event that a scheduled visit is missing. If there are multiple unscheduled visits, the closest one to the projected date will be selected; if there are ties, the later measurement will be used.

| Parameter | Analysis Visit/Time Point Window |
|-------------------------|--|
| Labs | Study Day ± 3 days from Target Day Early termination (ET) visits are mapped to the nearest missing analysis visit, using the same window, after unscheduled visits are considered. |
| MRI | Day 85: Study Day ≥ 78 ; ET visits with Study Day ≥ 65 will be mapped to Day 85. Day 141: Study Day ≥ 113 |
| Histology Endpoints | Day 141: Any post-baseline |
| Fibroscan | Day 141: Any post-baseline |
| Vital Signs | Study Day ± 3 days from Target Day; ET visits are mapped to the nearest missing analysis visit, using the same window, after unscheduled visits are considered. |
| Anthropometric Measures | Study Day ± 3 days from Target Day (For body weight) Study Day ± 14 days from Target Day (For waist-hip ratio related parameters) ET visits are mapped to the nearest missing analysis visit, using the same window, after unscheduled visits are considered |
| ECG | Study Day ± 3 days from Target Day ; ET visits are mapped to the nearest missing analysis visit after unscheduled visits are considered using Study Day |
| PK | Depending on the time point, the window for each time point is specified in the PK sampling schedule. If multiple unscheduled records are available, the sample collected closest to the nominal time will be selected. If the distance is the same, the later one will be selected. |

Measurements from all protocol planned visits will be summarized in descriptive tables and figures. For PD endpoints that are analyzed using MMRM analysis, only measurements taken at

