8.4.1. Analysis of Histology

8.4.1.1. Histology Measurements from Central Reader

Endpoints of different histological responses will be summarized with the point estimates and 95% CIs of the proportions of subjects who meet the response criteria (defined in Sections 4.1.2, 4.2, and 4.4) at Day 141 using the Histology Biopsy Analysis Set.

Baseline, change from baseline in individual score including NASH CRN fibrosis score, ISHAK fibrosis score, NAS score, steatosis grade, lobular inflammation grade, and ballooning grade will be summarized using the Histology Biopsy Analysis Set and by subgroups. The proportions of

subjects who met ≥ 1 -point improvement in steatosis, ≥ 1 -point improvement in ballooning, ≥ 1 -point improvement in inflammation will be summarized in tables and plotted in bar charts.

Shift of fibrosis stage from baseline to Day 141 in CRN and ISHAK fibrosis scores will be summarized. Shift of individual NAS components from baseline to Day 141 will be summarized.

Bar charts of CRN and ISHAK fibrosis scores with baseline and Day 141 side by side may be presented.

A series of five horizontal black bars of varying lengths, decreasing from left to right, set against a white background. The bars are positioned in a staggered, non-linear fashion, creating a sense of depth or a visual timeline. The first bar is the shortest, followed by a longer one, then a very long one, then another long one, and finally a very short one on the far right.

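### The Part 2 histology response rates cover only subjects with paired biopsies, so they can overstate response in all treated subjects, and no all-dosed analysis is visible.

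*SAP*

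**What the plan says.** Part 2 is a single-arm cohort: "Part 2 is an open-label cohort that will enroll 20 subjects with biopsy-proven NASH and fibrosis" (protocol 4.2). Its primary efficacy endpoint (SAP Part 2, 4.1.2) is a yes/no histological response. Fibrosis improvement and NASH resolution are secondary histology endpoints (4.2).

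The Histology Biopsy Analysis Set holds Full Analysis Set subjects "who have both baseline (screening or eligible historical) and post-baseline biopsies" (SAP Part 2, 7.4). Section 8.4.1.1 summarises the response proportions and their 95% CIs "using the Histology Biopsy Analysis Set". Protocol 8.4 agrees: the proportions are estimated "using the biopsy analysis set". SAP Part 2 section 7.1 names histology as an exception to the uses of the Full Analysis Set.

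Missing second biopsies are foreseen. SAP Part 2 section 3.5 allows for a redacted share "of subjects who will not undergo the post-baseline liver biopsy".

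Some rules keep subjects in the analysis. Those who stop study drug remain in the study (protocol 6.1). Those who withdraw have an early termination visit with the Day 141 assessments where possible (protocol Table 6 footnotes; SAP Part 2 Appendix 12.1). The histology row of the visit-window table reads "Day 141: Any post-baseline" (SAP Part 2, 8.1.3).

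**The concern.** The plan expects missing data on its primary efficacy endpoint, and the only handling visible is exclusion. The reported proportion then describes subjects who came back for a second biopsy. Readers will tend to take it as the response after 20 weeks of treatment in everyone treated, and there is no control arm to put it in context. With 20 subjects, each one is worth 5 points.

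The reasons for withdrawal in protocol 6.2 include adverse events, noncompliance and withdrawn consent. Subjects lost for such reasons could plausibly respond less often than those who return. Protocol 4.2.4 says the Part 2 results should help guide dose selection in later studies with histological endpoints, so an optimistic rate could carry forward into planning.

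The Part 1 SAP (9.4.3.2) plans a control-based imputation analysis for missing MRI-PDFF, a secondary endpoint there. No counterpart is visible for the Part 2 primary endpoint.

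**Working it through.** **No plan figure to reproduce.** The missing share, the number of paired biopsies, the CI half-width and the assumed response rate are all redacted in SAP Part 2 section 3.5, which also says "no formal power calculations were used to determine the sample size in Cohort 7".

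**Inputs**
- N = 20 dosed subjects (protocol 4.2, assuming all who enrol are dosed).
- m = number without a second biopsy. This is an assumption: 1 to 5 of 20, or 5% to 25%.
- CI: exact binomial 95% (SAP Part 2, 8.1.2).

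**Step 1: distance between conventions.** With x responders among n = 20 - m paired subjects, the paired rate is x/n. Counting missing as non-response gives x/20, and counting missing as response gives (x + m)/20. The gap from the paired rate to the non-response rate is x/n - x/20 = (m/20)(x/n). For paired rates near 60%:

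| m | Paired rate (exact 95% CI) | Missing = non-response (exact 95% CI) | Missing = response | Gap, points |
|---|---|---|---|---|
| 1 | 11/19 = 57.9% (33.5 to 79.7) | 11/20 = 55.0% (31.5 to 76.9) | 12/20 = 60.0% | 2.9 |
| 2 | 11/18 = 61.1% (35.7 to 82.7) | 11/20 = 55.0% (31.5 to 76.9) | 13/20 = 65.0% | 6.1 |
| 3 | 10/17 = 58.8% (32.9 to 81.6) | 10/20 = 50.0% (27.2 to 72.8) | 13/20 = 65.0% | 8.8 |
| 4 | 10/16 = 62.5% (35.4 to 84.8) | 10/20 = 50.0% (27.2 to 72.8) | 14/20 = 70.0% | 12.5 |
| 5 | 9/15 = 60.0% (32.3 to 83.7) | 9/20 = 45.0% (23.1 to 68.5) | 14/20 = 70.0% | 15.0 |

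Over paired rates of about 40% to 80%, the gap runs from 2.1 points (8/19 = 42.1% against 8/20 = 40.0%) to 20.0 points (12/15 = 80.0% against 12/20 = 60.0%). The paired rate always lies between the two all-dosed bounds.

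**Step 2: bias against the rate in all dosed subjects.** Let p be the response probability in subjects with a second biopsy and q that in subjects without one. The all-dosed rate is [(20 - m)p + mq]/20, so the expected bias of the paired rate is p minus this, which equals (m/20)(p - q). With p = 0.6:

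| m | q = 0 | q = 0.25 | q = 0.6 | q = 1 |
|---|---|---|---|---|
| 2 | +6.0 | +3.5 | 0 | -4.0 |
| 4 | +12.0 | +7.0 | 0 | -8.0 |

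For m = 2 and q = 0, for example, (2/20)(0.6 - 0) = 0.06, or +6 points.

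**Step 3: scale.** The largest exact 95% CI half-width is 22.8 points at n = 20, 24.0 at n = 18 and 26.1 at n = 15. In most of these scenarios the shift is smaller than the sampling error. The interval does not reflect it, however, because it conditions on having a second biopsy.

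**The case against.** The case for the plan is a fair one. The paired set is pre-specified and identical in protocol and SAP, and the sample size allows for missing biopsies. Part 2 is a first look at histology, with no power calculation and no specified test of the response rate. Section 8.3.1 tabulates the size of each analysis set and the reasons for discontinuation, so a reader could divide the responders by all dosed subjects. These points limit the severity. They do not make a paired-biopsy rate describe everyone treated, and a reason for leaving the study is not always the reason a biopsy is missing.

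Four stronger readings are tempting, and the documents do not support them.

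- **That early stoppers are dropped.** Subjects who stop drug stay in the study, the early termination visit mirrors Day 141 where possible, and any post-baseline biopsy is mapped to Day 141. Only dosed subjects with no second biopsy are lost. (The Table 6 visit headings are redacted, so the early termination biopsy is inferred from the footnotes and the window table.)
- **That the rate is biased upward.** The direction depends on q, which is not observed. COVID-19 disruption (protocol Appendix 5) is a documented reason for missing data that need not relate to response.
- **That no analysis counts the missing subjects.** The exploratory endpoints and part of the text after 8.4.1.1 are redacted, so only the absence of a visible analysis can be stated.
- **That an off-window biopsy should be scored as a failure.** That would answer a different question. Such biopsies are still performed, and are recorded and listed as protocol deviations.

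**Conclusion.** The point holds in limited form. The primary and secondary histology rates are completer-type estimates. They can overstate response in all 20 treated subjects if those without a second biopsy respond less often, and no visible analysis shows by how much.

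The 2 to 20 points is the distance between two conventions under an assumed 1 to 5 missing biopsies and paired rates of about 40% to 80%. A reader might take it as the size of the bias, but it equals the bias only in the extreme case where no subject without a second biopsy would have responded. The 20-point end needs 25% missing and an 80% paired rate, and neither figure is in the visible documents. If every dosed subject has an evaluable second biopsy, the issue disappears.

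**What to change.** In SAP Part 2 section 8.4.1.1, add an analysis of the primary and secondary histology responses in the Full Analysis Set that counts a missing or unevaluable second biopsy as non-response, with the exact 95% CI. Report it beside the paired-biopsy analysis, together with the number of missing second biopsies and the reason for each. Align section 7.1, which at present excludes histology from the Full Analysis Set.

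Optionally, add a sensitivity analysis limited to biopsies taken within 14 days after the last planned dose (Day 134), since the window row sets no time limit. This restricts the set and does not score other biopsies as non-response.

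The cost is SAP wording and one extra table (a second if the timing analysis is added), with no new data or procedures. The downside is a second rate that will be somewhat lower than the first whenever a biopsy is missing. Label: cheap improvement.

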8.1. General Considerations

In general, scheduled visits from baseline to Day 162 will be summarized. For summaries of worst post-baseline or post-baseline min/max, all visits will be considered, including unscheduled.

8.1.1. Statistical Notation and Presentation

All data collected from all subjects in the electronic data capture will be presented in the subject level listings. All continuous data will be listed with the same precision as presented in the

database. Data listings will be sorted by subject ID and time point. Missing values will be represented by an empty cell and no imputation will be made. If imputation is used for analysis, excluding treatment-emergent and concomitant medication determinations, the imputed values will be listed with a derivation type column in the listing indicating that origin of the imputed value.

Continuous data will be summarized in tables using number of subjects or sample size (n), mean, median, standard deviation (SD), minimum and maximum.

Categorical data will be summarized in two ways, by subject and by time point. Subject data will be summarized using the count of distinct subjects that fall in the category and the percentage of the total number of subjects. Population counts, either the number of subjects or the number of assessments at the time point, will be used as the denominator in the calculation of percentages unless specified otherwise.

The original units (conventional) and SI units will be presented in listings. In general, conventional units will be used for tables and figures, unless otherwise specified. Insulin will use the conventional unit of uU/mL; estimated glomerular filtration rate will be presented using SI units.

Minimum and maximum values will use the precisions of the original value. Means, least-squares (LS) means, and medians will be rounded to one decimal place greater than the precision of the original value up to a max of two decimal places. The limits of confidence intervals (CI), standard deviations (SD), and standard errors (SE) will be rounded to two decimal places greater than the precision of the original value. Derived PK and PD data (e.g., unit conversion) will be presented with three decimal places. Percentages will be rounded to the nearest tenth. Two-sided p-values will be presented with four decimal places and values less than 0.0001 will be presented as <.0001.

8.1.2. Inferential Statistical Analysis Methods

A mixed-model repeated measures (MMRM) analysis will be used to analyze the change from baseline and/or percent change from baseline for selected PD parameters. The model will include baseline value of the dependent variable as a covariate, and subjects as a random effect to account for repeated visits. A compound symmetric covariance structure will be used. The LS means will be derived from the model with their corresponding SE, p-values and two-sided 95% CI.

If strong evidence exists that the normality assumptions are violated for, but not limited to, triglycerides or MRI-PDFF, non-parametric methods will be considered such as the Wilcoxon Rank Sum test.

For proportion of various types or responders, the 95% exact binomial CI will be provided.

The Cohen-Kappa statistics, including the Kappa coefficient, 95% CI, and two-sided p-value will be applied when assessing the concordant and discordant between two raters, e.g., histology data central reader versus PathAI reader.

There will be no adjustments for multiplicity in this study.

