8. STATISTICAL CONSIDERATIONS

This section describes the statistical analysis as foreseen at the time of planning the study. Changes, additions, and further details about the analyses will be described in the statistical analysis plan, if applicable. Any subsequent additional analyses or changes to analyses that may be required will be fully disclosed in the clinical study report. Summaries and analyses will be presented by dose/treatment group for Part 1 and separately for Part 2. Before database lock, final statistical and pharmacokinetic analysis plans containing full details of all planned analyses will be produced. The analyses presented here represent an outline of the intended methodology. Details of the analysis will be described in a Statistical Analysis Plan. All clinical data will be summarized using descriptive statistics: number (n), mean, standard deviation (SD), median, minimum, and maximum for continuous measurements, and counts and percentages for categorical measurements.

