3.1. Study Design

Part 2 of study BIO89-100-002 is an open-label cohort (Cohort 7) in which BIO89-100 will be administered SC weekly at a single dose level (27 mg QW) to approximately 20 subjects with biopsy-proven NASH (NAS ≥ 4 , fibrosis stage F1 with high risk, F2 or F3), to evaluate effect on histological endpoints.

| Cohort | Dose Level ^a | Frequency and Route of Administration | Number of Subjects | |
|--------|-------------------------|---|--------------------|---------|
| | | | BIO89-100 | Placebo |
| 7 | 27 mg | QW, SC to abdomen (2 injections) Days 1, 8, 15, 22, 29, 36, 43, 50, 57, 64, 71, 78, 85, 92, 99, 106, 113, 120, 127, and 134. Total doses: 20 | 20 | NA |

^aThe actual doses will be $\pm 5\%$ the mg dose due to technical considerations related to drug withdrawal from the vials into the syringes for injection. This difference is considered negligible for subject exposure.

The study will include a Screening period, a Treatment period, and a Follow-up period. After signing informed consent, subjects will undergo screening assessments to determine eligibility over a period of up to 60 days.

For each subject in Part 2 (Cohort 7), the total duration of study participation will be up to 229 days (31.5 weeks), excluding the potential study interruption due to the Coronavirus disease 2019 (COVID-19) pandemic:

- Screening period: ≤60 days (8.5 weeks)
- Treatment period: 141 days (20 doses in 19 weeks)
- Follow-up period 28 days (4 weeks)

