3.3. Randomization Schedule and Blinding Procedures

Part 2 will be open-label with all subjects receiving the same dose (i.e., 27 mg SC QW) of BIO89-100.

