3.4. Stratification Factors

There are no stratification factors for Part 2.

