5.10. Definition of the Open-Label Treatment Group

The definition of the open-label treatment group is BIO89-100 27 mg QW.

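### Part 2 has one arm, but the only non-parametric alternative its SAP names is the two-sample Wilcoxon rank-sum test, which cannot replace an analysis of change from baseline

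*SAP*

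**What the plan says.** The Part 2 design has one group. Section 3.1 of the Part 2 SAP plans dosing "to approximately 20 subjects with biopsy-proven NASH", with the placebo column marked not applicable. Section 3.3 states: "Part 2 will be open-label with all subjects receiving the same dose (i.e., 27 mg SC QW) of BIO89-100". Section 5.10 defines the only group: "The definition of the open-label treatment group is BIO89-100 27 mg QW". Section 3.4 adds: "There are no stratification factors for Part 2". Protocol section 8 keeps the two parts apart: "Summaries and analyses will be presented by dose/treatment group for Part 1 and separately for Part 2".

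Triglycerides and MRI-PDFF are secondary endpoints in Part 2 SAP section 4.2, each as change and percent change from baseline. Section 8.1.2 analyses them with an MMRM: "The model will include baseline value of the dependent variable as a covariate, and subjects as a random effect to account for repeated visits". There is no treatment term. The output is within-group: "The LS means will be derived from the model with their corresponding SE, p-values and two-sided 95% CI".

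The next paragraph gives the alternative. Given strong evidence that normality fails, for endpoints including these two, "non-parametric methods will be considered such as the Wilcoxon Rank Sum test". The same clause stands in Part 1 SAP section 9.1.2.

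**The concern.** An alternative to an MMRM should answer the question the MMRM answers. Here that is whether change from the subject's own baseline differs from zero at a given visit. The rank-sum test asks whether two independent samples come from the same distribution. Part 2 supplies one column of changes per visit and no comparator.

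Two things could follow if the alternative were invoked. The test may prove impossible to run on the planned variable, so that the real test is picked after open-label data have been seen. Or someone may make it run by entering baseline and post-baseline values as two groups. That discards the pairing, drops the planned change and percent-change variables, and gives a p-value resting on an independence assumption that is false by design.

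**Working it through.** **No plan figure to reproduce.** The point concerns the type of test. The Part 2 SAP gives no power calculation, and its precision inputs are blacked out.

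**Step 1: does the test fit?** In Part 1 the rank-sum test has groups to compare. Part 1 SAP sections 9.4.2.1 (triglycerides) and 9.4.3.4 (MRI-PDFF) compare change by treatment group, and the code in 13.1 uses treatment as the class variable. The matching Part 2 sections, 8.4.3.1 and 8.4.4, present change by visit in one cohort. Their readable text schedules no non-parametric analysis. No readable Part 2 text names a signed-rank, sign or other one-sample method.

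**Step 2: why the misuse is conservative.** Inputs: n = 20 (Part 2 SAP 3.1) and nominal two-sided 5%. The correlation r between baseline and follow-up and the size of the shift are assumptions; the documents give neither. With no true change, positive correlation shrinks the variance of the rank-sum statistic by a factor of 1 − ρs, where ρs = (6/π)·arcsin(r/2) for bivariate normal data or any increasing transformation of them. In large samples:

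true size ≈ 2Φ(−1.96/√(1 − ρs))

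- r = 0.5: ρs = 0.483, √(1 − ρs) = 0.719, 1.96/0.719 = 2.73, size 0.6%
- r = 0.7: ρs = 0.683, √(1 − ρs) = 0.563, 1.96/0.563 = 3.48, size 0.05%
- r = 0.8: ρs = 0.786, √(1 − ρs) = 0.463, 1.96/0.463 = 4.24, size 0.002%

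At n = 20 the approximation is somewhat too small at high r. Simulation gives about 0.05% to 1% across this range.

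**Step 3: why pairing gains power.** The SD of the change is √(2(1 − r)) times the single-visit SD: 1.00, 0.77 and 0.63 for r = 0.5, 0.7 and 0.8. A shift of 0.4 SD is therefore 0.40, 0.52 and 0.63 SD of the change. The signed-rank test uses that gain.

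**Step 4: simulation.** Pairs were bivariate normal on the log scale and exponentiated to give skew, with n = 20 and a 0.5 SD shift. The rank-sum test was run on baseline versus follow-up values (10,000 runs) and the signed-rank test on within-subject log change (4,000 runs).

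| r | Size, rank-sum | Size, signed-rank | Power, rank-sum | Power, signed-rank |
|---|---|---|---|---|
| 0 | 5.0% | 4.9% | 32% | 31% |
| 0.3 | 2.2% | 4.5% | 29% | 41% |
| 0.5 | 0.6% | 4.7% | 27% | 54% |
| 0.7 | 0.1% | 4.3% | 24% | 76% |
| 0.8 | 0.0% | 4.5% | 22% | 90% |

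With n = 16 (also an assumption) and r = 0.7, size is 0.15% versus 4.8% and power 17% versus 64%.

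**Step 5: range of shifts.** Bivariate normal data, n = 20, r from 0.5 to 0.8:

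| Shift | Power, signed-rank | Power, rank-sum |
|---|---|---|
| 0.4 SD | 38-76% | 10-17% |
| 0.6 SD | 69-97% | 39-46% |
| 1.0 SD | 99-100% | 91-98% |

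**The case against.** The best defence is that nothing is committed. The sentence needs strong evidence first, then says only that methods will be considered, and gives the rank-sum test as an example. A signed-rank test already falls under non-parametric methods, and section 1 of the Part 2 SAP allows deviations with a sound statistical rationale. A programmer handed one column of changes would probably notice and switch. All of this stands, and it limits the point to a wording correction. It does not make the example usable.

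A reader might infer more than the documents support:

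- *That the SAP expects these endpoints to be non-normal.* It names them conditionally and says nothing about likelihood.
- *That the test can only be run by misusing paired data.* It could validly compare two subgroups of Cohort 7. Protocol section 4.2.2 plans work in MRI-PDFF responders, and some Part 2 SAP text is blacked out. But that would answer a different question from the MMRM it is offered to replace.
- *That no estimate of change would be reported.* Sections 8.1.1, 8.4.3.1 and 8.4.4 provide descriptive summaries of change and percent change, including medians, and MRI-PDFF responder proportions carry 95% CIs. What is missing is a non-parametric estimate of change with its interval.
- *That a real MRI-PDFF effect would be missed.* Protocol section 2.3.3 reports that up to 88% of treated Part 1 subjects reached a 30% reduction. No SD is given, but this suggests a large shift, where little power is lost.

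**Conclusion.** The point holds as a wording error of limited consequence. The only non-parametric method that Part 2 SAP section 8.1.2 names needs two independent samples, and the analysis it would replace has one sample of within-subject changes. That conclusion rests on the documents alone.

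The numerical cost depends on a misuse that the plan does not prescribe and on assumed correlations and shifts. In that case the test would rarely reject under no change and would lose much power for moderate effects, but little for large ones. Because the error is conservative, it would not manufacture a claim of benefit. The endpoints are secondary, in an open-label cohort with no multiplicity control. The primary histology endpoint is reported with exact binomial intervals and is untouched.

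The identical clause in Part 1 suggests that the sentence was carried over. That is an inference from the wording, not something the documents state.

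**What to change.** In Part 2 SAP section 8.1.2, replace the reference to the rank-sum test with the Wilcoxon signed-rank test of change and percent change from baseline against zero, by visit, reported with the one-sample Hodges-Lehmann estimate and its 95% CI. The test assumes that changes are roughly symmetric about their centre, so a half-sentence saying so would help whoever applies it to triglycerides. The Part 1 wording can stay. The cost is one sentence in the SAP: no new data, no change in design or sample size, and no effect on the primary analysis.
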